The study is a single-site, participant-blinded, pilot study for up to 60 patients in the Westlake dermatology clinic. Using the pen-like VAD, vibration will be applied with cotton on an anatomical site of one side (right or left) and without cotton on the same anatomical site on the other side. To fix cotton to the VAD, a cotton ball will be positioned at the tip of the VAD with placement into a nitrile glove (5). The VAD we are using for this procedure is the current standard of care and is not a novel device.

The anatomical sites were chosen in terms of sites with minimal subcutaneous fat and areas where patients have anecdotally reported discomfort with the VAD. The sites will be the lateral nasal wall, sub-malar region of the cheek, ear helix, lateral neck, and dorsal side of the forearm.

The order of the five anatomical sites and the order of conditions (VAD and VAD with cotton) will be randomized, and all possible orders will be placed into an envelope. One envelope will be randomly selected for each patient to determine the order of anatomical sites and order of condition for that particular patient. The patients will be blinded to what treatment is applied. For example, patients will be instructed to close their eyes or to look away from the application site.

There will be 10 total applications (VAD and VAD with cotton for five anatomical sites) each subject will undergo. Each application of the VAD will last for 20 seconds. Between each VAD application, there will be a delay of 10 seconds. After applying vibration to the same anatomical sites on the left and right side, patients will be asked which of the two treatments was preferred, which should take around one minute. To monitor participants for safety, participants will be encouraged to report any discomfort or adverse effects they experience during or after each vibration and after each VAD application, participants will be asked if they are ready to move on to the next one.

Before completion of the protocol, but after the informed consent, patients will be asked questions regarding their medical history. Additionally, before administering vibrations, patients will be trained to distinguish between small and large dowels, applying the minimum amount of pressure, while their eyes are closed to ensure accurate perception of the vibration.

Data will be patient reported and will be collected in a secure RedCap online database.

Study Timeline

Estimated time requirement of visit	Visit 1

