Patient Screening and Informed Consent	10 minutes
Data Collection	15 minutes
Anatomical site vibration (10)	15 minutes

Data to be Collected for your study

The study will collect sociodemographic information, including age, gender, and race, to understand the generalizability of data. Medical history data will encompass past medical conditions, history of prior procedures, and any previous use of vibration before injection. Patient chart will be looked at for the purpose of validating patient survey questions. Chronic pain history will be recorded, including the participant's relationship with a chronic pain specialist, current use and duration of pain medication, the specific medication used, and the

type, location, and duration of chronic pain. The presence, history, and location of neuropathy will also be documented. Lastly, the primary outcome variable will assess participant preference for each anatomical site, comparing the use of cotton versus no cotton.

Data Analysis Plan

As this is a pilot study, we are not able to conduct a power analysis. However, similar studies at UH using this same VAD have a similar target of up to 60 patients. A binomial test will be used to determine whether the proportion of participants preferring cotton differs significantly from the expected 50/50 baseline for each anatomical site. Additionally, Chi-Square Tests of Independence will be conducted to assess whether preferences for cotton versus no cotton vary based on participant characteristics, including chronic pain status, neuropathy status, or anatomical site. Qualitative data on the reason behind preference will be asked and independently categorized by at least two raters.

Risks to Research Participants

Minor discomfort may be experienced by patients from vibration for a few seconds per site. Additionally, there might be an anxiety due to potential discomfort. There will also be a risk of breach of confidentiality. Participants will be informed that they can withdraw from the study at any time without penalty.

Provisions to Protect the Privacy Interests of Research Participants

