Vibration tests will occur in private rooms. All collected data will be de-identified in RedCap, ensuring that no personally identifiable information is linked to study responses. Data will be securely stored in a password-protected, restricted-access database of REDCap, with access limited to authorized research personnel only. A coding system will be used, where a unique participant code is linked to each subject's data. Only authorized research personnel will have access to this code, and it will be securely stored separately from the study data in a linking log.

Potential Benefit to Research Participants

There is no direct benefit to research participants. Indirectly, if the use of cotton with vibration proves to be more comfortable for patients, it could provide a simple, cost-effective, and widely implementable solution for VAD use which optimizes patient comfort. This could be especially

beneficial for individuals with heightened pain sensitivity, such as those with chronic pain or neuropathy.

Withdrawal of Research Participants

Participants will be withdrawn from the study if they experience unexpected or intolerable discomfort that prevents them from completing the procedure. Additionally, participants may be withdrawn if they do not follow study instructions properly, which could compromise the integrity of the data collection process. If a participant withdraws before completing the procedure, their data will not be included in the study analysis. If a participant is withdrawn due to noncompliance or intolerable discomfort, their collected data will be discarded. Participants will be informed of their right to withdraw at any time without penalty.

Alternatives to Participation

The alternative to participation is not to participate.

Drugs or Devices

The pen-like vibratory anesthetic device which is the current standard of care in UH dermatology clinics and is not a novel device will be the main device used for this study on 5 anatomical sites each on the left and right side.

Additional Information

This VAD used is a current standard of care for dermatologic procedures, and this is not a novel device.

Community-Based Participatory Research

This is not community-based participatory research.

References

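### All data from anyone who stops early are dropped, so up to four completed site preferences per stopper are lost and every site's estimate describes full completers only

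*Combined protocol and SAP*

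**What the plan says.** Two consecutive sentences in Withdrawal of Research Participants cover every early stop. For participants who leave by choice: "If a participant withdraws before completing the procedure, their data will not be included in the study analysis". For those taken out by the study team: "If a participant is withdrawn due to noncompliance or intolerable discomfort, their collected data will be discarded". Neither makes an exception for sites already finished.

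Study Procedures sets the session length: "There will be 10 total applications (VAD and VAD with cotton for five anatomical sites) each subject will undergo". Once both sides of a site have been treated, "patients will be asked which of the two treatments was preferred", so each completed pair yields one answer. The order of sites is randomized for each patient.

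Data to be Collected defines the primary outcome site by site: "Lastly, the primary outcome variable will assess participant preference for each anatomical site, comparing the use of cotton versus no cotton". The Data Analysis Plan applies a binomial test to find out "whether the proportion of participants preferring cotton differs significantly from the expected 50/50 baseline for each anatomical site". Chi-square tests are also planned on whether "preferences for cotton versus no cotton vary based on participant characteristics, including chronic pain status, neuropathy status, or anatomical site".

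Data to be Collected does not list stops, or the site, condition or reason for them. Study Procedures invites participants to report discomfort and checks that they are ready to continue after each application, but as safety monitoring; no analysis use is stated.

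**The concern.** The primary test at a site needs only that site's pair. A participant who finishes three sites and stops in the fourth has given three valid primary answers, and the rule deletes all three. With at most 60 participants, these are answers already obtained.

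The rule also changes whom each estimate describes: people who completed all 10 applications, rather than people who were tested at that site. Intolerable discomfort is a named ground for deletion, and comfort is what the trial studies, so stopping may be related to preference. The documents do not establish that link. But because stops and their circumstances are not among the listed data, the plan offers no way to check whether the exclusion moved the estimates. A count of discomfort stops by condition would itself be useful preliminary data on comfort.

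Excluding the whole person for noncompliance is not disputed here.

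**Working it through.** **Answers lost per stopper.** Applications: 5 sites × 2 conditions = 10, which reproduces the plan's figure. A person who stops after *k* applications (*k* = 0 to 9) has at most floor(*k*/2) completed pairs: 0, 1, 2, 3 or 4. So up to four answers are deleted, and an average of 2 if the stop is equally likely in each of the five pairs.

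**Assumptions.** The documents give no stop count, significance level or sidedness. Assumed here: 60 enrolled, two-sided 0.05, and one, three or six stops.

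**Bias.** Let *s* be the share who stop, and *pc* and *ps* the cotton preference of completers and stoppers. The all-enrolled proportion is (1 − *s*)·*pc* + *s*·*ps*, so the completers-only estimate is off by *s*·(*pc* − *ps*). For a 20-point difference:

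- no stops: 0
- one stop: (1/60) × 20 = 0.3 points
- three stops: (3/60) × 20 = 1.0 point
- six stops: (6/60) × 20 = 2.0 points

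The extremes with three stops and 37/57 completers preferring cotton are (3/60) × (64.9 − 0) = +3.2 points and (3/60) × (64.9 − 100) = −1.8 points.

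**Effect on a site's test** (exact two-sided binomial against 0.5, three stops). The bounds count all three missing answers as no cotton, then all as cotton.

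| Completers preferring cotton | All missing = no cotton | All missing = cotton |
|---|---|---|
| 37/57 (64.9%), p = 0.033 | 37/60 (61.7%), p = 0.093 | 40/60 (66.7%), p = 0.014 |
| 42/57 (73.7%), p = 0.0005 | 42/60 (70.0%), p = 0.0027 | 45/60 (75.0%), p = 0.0001 |
| 30/57 (52.6%), p = 0.79 | 30/60 (50.0%), p = 1.00 | 33/60 (55.0%), p = 0.52 |

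Only the first row, chosen close to the threshold, can change. Above 50%, the completer counts at which some pattern of missing answers changes the result are 38 of 59 with one stop, 36 to 38 of 57 with three, and 33 to 38 of 54 with six.

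**How often that matters.** The middle columns give the chance that the completer count falls in the range where the result *could* change (both tails). The last column gives the chance that it *does* differ from the all-enrolled result with three stops, for stoppers' preference 20 points below to 20 points above completers'.

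| Completers' true preference | Could change, one stop | Could change, three stops | Does change, three stops |
|---|---|---|---|
| 50% | 2% | 5.5% | 1.3–1.6% |
| 65% | 11% | 32% | 6.4–9.1% |
| 75% | 2% | 8% | about 1–2% |

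**What keeping completed pairs recovers.** With three stops, the current rule leaves 3 answers missing per site: 3/60 = 5.0 points of unknown range. If completed pairs are kept, the average missing per site is 3 (all stop in the first pair), 1.8 (stops spread evenly) or 0.6 (all stop in the last pair), giving 5.0, 3.0 or 1.0 points.

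**The case against.** The case for leaving the rule alone is mainly about size. The Risks section expects little trouble ("Minor discomfort may be experienced by patients from vibration for a few seconds per site"), each application lasts 20 seconds with a device already in standard use, and eligibility requires being able to complete the session. Stops should be few. A 1.0-point bias is small beside a standard error of about √(0.65 × 0.35/60) = 6.2 points. The 32% figure is only an upper limit: the actual chance of a changed result is 6.4% if stoppers share completers' preference and 9.1% if theirs is 20 points lower. Most of that reflects having fewer answers, not selective exclusion. All of this stands, and it limits the severity.

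A completers-only set also keeps the same people at all five sites, which helps the between-site comparison. That is a real advantage, but a sensitivity analysis preserves it; the single-site binomial tests do not need it.

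The consent wording is not in the text reviewed, and discarding data might reflect a promise made to participants. The proposed change must therefore defer to it.

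Finally, keeping completed pairs recovers nothing from someone who stops in the first pair. That is correct, and is why bounds are proposed as well.

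None of these points gives a reason to delete answers already given at finished sites, or to leave stops out of the listed data.

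**Conclusion.** The concern holds and should be fixed. The rule as written deletes up to four valid primary answers per early stopper, restricts every site's estimate to full completers, and does so partly for a reason tied to the study question. This follows from the text and does not depend on how many people stop.

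The numerical consequence does depend on that, and is probably modest: 0.3 to 2.0 points of bias for one to six stops among 60 with a 20-point preference difference, all of which are assumptions. The direction cannot be determined from the documents, and the bias is zero if nobody stops or if preferences match. A test result is at risk only for a site already near the threshold.

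**What to change.** Leave the rule for when a participant stops, and the exclusion for noncompliance, unchanged.

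1. At each site, analyse every completed left-right pair, including those from participants who stop early for discomfort or any other reason except noncompliance, as far as the consent wording allows and unless the participant asks for removal. Keep a completers-only analysis as a sensitivity check, particularly for the comparison between sites.
2. Add the site, condition and reason at stopping to Data to be Collected, and report discomfort stops by condition.
3. At each site, give best- and worst-case bounds for pairs missing because of discomfort stops: all counted as cotton, then all as no cotton.

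The cost is revised protocol and analysis wording, a check against the consent form, a few extra data fields and a little more analysis. Denominators will differ slightly between sites and the people analysed will not be identical, which the completers-only check addresses. No extra patients or procedures are needed. The change should be made before any data are discarded, since deletion may not be reversible.
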